6.2.3 Follow up period and trial completion

A follow up visit will be performed 7 days (+7 day window) after the last dose of trial medication. The assessments to be performed at the follow-up visit are indicated in the [Flow Chart](#). The follow-up visit marks the completion of the study for the individual patient.

See [section 3.3.4.1](#) for procedures to be followed in case a patient prematurely discontinues trial treatment.

7. STATISTICAL METHODS AND DETERMINATION OF SAMPLE SIZE

7.1 STATISTICAL DESIGN - MODEL

The eligible patients for this trial will be randomised to empagliflozin 10 mg and placebo in 1:1 ratio.

The primary endpoint is the change from baseline to week 12 in exercise capacity as measured by the distance walked in 6 minutes. The statistical model will be a Wilcoxon rank test on change from baseline to week 12 in distance walked in the 6MWT.

The primary model will be conducted on all randomized patients. Where more than one measurement is available on the same day (duplicate measurements), the highest distance walked will be used for analysis.

The two key secondary endpoints 'Change from baseline to week 12 in KCCQ-TSS' and 'Change from baseline to week 12 in CHQ-SAS dyspnea score' are part of the testing strategy.

Both key secondary endpoints will be tested using a Wilcoxon rank test, and both will be tested if the primary endpoint revealed a significant result in favour of empagliflozin. For adjustment of multiplicity of the two key secondary endpoints a Hochberg procedure will be followed.

The other secondary endpoints will not be part of the testing hierarchy.

7.2 NULL AND ALTERNATIVE HYPOTHESES

Both key secondary endpoints will be tested if the primary endpoint revealed a significant result in favour of empagliflozin. For adjustment of multiplicity of the tests of the two key secondary endpoints a Hochberg procedure will be followed. The trial is designed to achieve a power of 90% for the primary endpoint at level $\alpha = 0.05$ to detect a difference between empagliflozin and placebo.

For all endpoints, superiority of empagliflozin vs. placebo will be evaluated with a two-sided test in the following structure:

Null hypothesis: There is no difference between the effect of placebo and the effect of empagliflozin in terms of the endpoint in question.

Alternative hypothesis: There is a difference between the effect of placebo and the effect of empagliflozin in terms of the endpoint in question. The tests will be performed in the

following hierarchical order:

1. Change from baseline to week 12 in exercise capacity as measured by the distance walked in 6 minutes
2. Hochberg procedure of :
 - Change from baseline to week 12 in KCCQ TSS
 - Change from baseline to week 12 in CHQ-SAS dyspnea score

If the null hypothesis for the primary analysis is rejected, and the result is more favourable for empagliflozin, superiority is concluded in the primary endpoint, and the overall type I error is preserved for the test in the next step.

In the next step a Hochberg procedure will be applied to account for multiplicity of testing of the key secondary endpoints.

If the primary hypothesis is not rejected, the tests of the key secondary endpoints are conducted in an exploratory fashion.

The other secondary endpoints will be evaluated in an exploratory manner.

7.3 PLANNED ANALYSES

The efficacy analysis will be based on the randomised set (RS), including all randomised patients.

The safety analysis will be based on the treated set (TS), which consists of all patients treated with at least one dose of the trial medication.

For both efficacy and safety analyses, treatment will be evaluated as randomised.

For serum creatinine and values based on upon this measurement such as eGFR, baseline will be defined as the mean of all available measurements from the screening visit until start of randomised trial medication.

For all other endpoints, baseline will be defined as the last available measurement before start of randomised trial medication.

Note that for the primary endpoint the higher measurement for each day is selected as the test result for that day. Therefore the last available measurement before start of trial medication will refer to the higher value on the day of the last measurement before treatment intake.

7.3.1 Primary endpoint analyses

The primary endpoint ‘change from baseline to week 12 in exercise capacity’ will be evaluated using a normal approximation of the Wilcoxon rank test using the randomized set. For estimation of effect the non-parametric Hodges-Lehmann estimate for the median difference will be calculated. Any confirmatory conclusion such as for hierarchical testing will be based on the result of the Wilcoxon rank test and will not consider the Hodges-Lehmann estimate or the corresponding confidence interval, which are given to support interpretation.

If repeated distance walked in 6 minutes (6MWT) measurements on the same day are available the longest distance will be used for this day.

Change from baseline will be defined as distance walked in 6 minutes (6MWT) at week 12 assessment minus the distance walked at baseline.

If no value for the 6MWT is available at week 12, an imputed value as defined in [table 7.5: 1](#) will be used.

Sensitivity analysis for the primary endpoint will include using a mixed model repeated measure analysis (MMRM) with baseline 6MWT as a covariate without imputation of missing values.

7.3.2 Secondary endpoint analyses

Key secondary endpoints

Both key secondary endpoints ‘Change from baseline to week 12 in heart failure symptoms as measured by the KCCQ TSS’ and ‘Change from baseline to week 12 in CHQ-SAS dyspnea score’ will be evaluated using a normal approximation of the Wilcoxon rank test using the randomized set. For estimation of effect the non-parametric Hodges-Lehmann estimate for the median difference will be calculated.

Change from baseline in both scores will be defined as the endpoint value at week 12 minus the last available endpoint value before start of randomised trial medication.

If no questionnaire is available at week 12, an imputed value as defined similar to the imputation for the primary endpoint will be used.

Sensitivity analysis for the key secondary endpoint will include using a mixed model repeated measure analysis with baseline of the key secondary endpoint as a covariate without imputation of missing values.

Other secondary endpoints

Change from baseline to week 6 in exercise capacity as measured by the distance walked in 6 minutes will be evaluated using the same model as for the primary endpoint.

Change from baseline of Clinical Congestion Score at week 12 will be evaluated using a mixed model repeated measure analysis (MMRM) analysis over time. The model will include the factor treatment and the linear covariate of baseline Clinical Congestion Score.

Proportion of patients in every category of global impression of change at week 12 will be evaluated using Cochran-Mantel-Haenszel test. Details on combining categories if the proportion of patients in one of the categories is small will be given in the TSAP.

Proportions of patients categorized by the shift in scores between baseline and week 12 in patient global impression of severity score will be evaluated using Cochran-Mantel-Haenszel test. Details on combining categories if the proportion of patients in one of the categories is small will be given in the TSAP.

The endpoint “Change from baseline in NT-proBNP at week 12” (after log-transformation) will be evaluated using a MMRM analysis over time with baseline log-transformed NT-proBNP as a covariate without imputation of missing values.

7.3.3 Further endpoint analyses

Endpoints describing responders such as increase in 6MWT \geq 30 m or response in KCCQ or CHQ domains will be evaluated using a Chi-Square test.

Proportions of patients categorized by the shift in scores between baseline and week 6 in patient global impression of severity score will be evaluated using Cochran-Mantel-Haenszel test. Details on combining categories if the proportion of patients in one of the categories is small will be given in the TSAP.

Proportion of patients in every category of patient global impression of change at week 6 will be evaluated using Cochran-Mantel-Haenszel test. Details on combining categories if the proportion of patients in one of the categories is small will be given in the TSAP.

Proportion of patients in every category in clinician global impression of change at week 6 and week 12 will be evaluated using Cochran-Mantel-Haenszel test. Details on combining categories if the proportion of patients in one of the categories is small will be given in the TSAP.

Proportions of patients categorized by the shift in scores between baseline and week 6 (week 12) in clinician global impression of severity score will be evaluated using Cochran-Mantel-Haenszel test. Details on combining categories if the proportion of patients in one of the categories is small will be given in the TSAP.

Change from baseline continuous endpoints such as KCCQ domains or CHQ domains at week 6 and Week 12 will be evaluated using a MMRM analysis over time. The model will include treatment as fixed categorical effect and baseline of the respective endpoint as fixed continuous effect.

Change from baseline in Clinical Congestion Score at week 6 will be evaluated by the same MMRM used to evaluate Clinical Congestion Score at week 12 described for the secondary endpoint.

Change from baseline in NT-proBNP at week 6 will be evaluated by the same MMRM used to evaluate NT-proBNP at week 12 described for the secondary endpoint.

Proportions of patients categorized by the shift in scores between baseline and week 12 in NYHA class will be evaluated using Cochran-Mantel-Haenszel test. Details on combining categories if the proportion of patients in one of the categories is small will be given in the TSAP.

Change from baseline to week 12 in patient-rated assessment of dyspnea and fatigue by the Borg scale as part of the 6MWT will be presented descriptively.

Other further endpoints will be analysed descriptively.

7.3.4 Safety analyses

Adverse events will be coded using the Medical Dictionary for Drug Regulatory Activities (MedDRA). Standard BI summary tables and listings will be produced. All adverse events with an onset between start of treatment and end of the residual effect period (REP), a period of 7 days after the last dose of trial medication, will be assigned to the on-treatment period for evaluation.

All treated patients will be included in the safety analysis. In general, safety analyses will be descriptive in nature and will be based on BI standards. No hypothesis testing is planned.

Statistical analysis and reporting of adverse events will concentrate on treatment-emergent adverse events, i.e. all adverse events occurring between start of treatment and end of the residual effect period. Adverse events that start before first drug intake and deteriorate under treatment will also be considered as 'treatment-emergent'.

Frequency, severity, and causal relationship of adverse events will be tabulated by system organ class and preferred term after coding according to the current version of the Medical Dictionary for Drug Regulatory Activities (MedDRA) at the database lock.

Laboratory data will be analysed both quantitatively as well as qualitatively. The latter will be done via comparison of laboratory data to their reference ranges. Values outside the reference range as well as values defined as clinically relevant will be summarised. Treatment

groups will be compared descriptively with regard to distribution parameters as well as with regard to frequency and percentage of patients with abnormal values or clinically relevant abnormal values.

Vital signs, physical examinations, or other safety-relevant data observed at screening, baseline, during the course of the trial and at the end-of-trial evaluation will be assessed with regard to possible changes compared to findings before start of treatment.

Reasons for discontinuation and use of post-baseline concomitant medications will be tabulated.

The details of the analysis will be specified in the Trial Statistical Analysis Plan (TSAP).

7.3.5 Pharmacokinetic and pharmacodynamic analyses

Not applicable.

7.4 INTERIM ANALYSES

No interim analysis is planned but a DMC will be in place with tasks as described in [section 8.7](#).

7.5 HANDLING OF MISSING DATA

Patients with an available week 12 measurement of the 6MWT, regardless of whether on or off-treatment, will be ranked based on change from baseline in 6MWT distance at week 12.

If a patient performs the visit at week 12 but is unable to walk or unable to perform the 6MWT due to safety concerns, then this will be noted accordingly in the case report form and will not be regarded as missing data. This case will be evaluated as a measured distance of 0m.

Missing data will be imputed according to the rules outlined in [table 7.5: 1](#), and ranks will be assigned based on the imputed data. Imputed data will also be used to calculate the Hodge Lehmann estimates for the median difference. Note that no imputation will be used in the MMRM analysis that serves as sensitivity analysis in this trial.

All imputed data due to missing data will be lower than measured values. The lowest measurable value of the primary endpoint of change from baseline in 6MWT distance is a reduction by 350m, i.e. the highest possible baseline value (350 m), and at week 12 the lowest possible value of 0m. Therefore, all imputed values for change from baseline for patients with missing walking distance at week 12 are below -350 m.

Table 7.5: 1 Imputation rules for missing primary endpoint

	Category	Ranking	Case description	Imputed change from baseline in 6MWT for described case (in m)*
1	Missing data on 6MWT at week 12 and no clinical event: Patients with missing 6MWT at week 12 and no event as in category 2 or 3	If post-baseline value is available, rank by last available value. Rank below if no post-baseline value is available	Patient has a change from baseline to last available value of x m, no clinical event	-352 +x/1000
			No information of post-baseline 6MWT distance and no clinical event	-354
2	Missing data and clinical event (except death). A clinical event is defined as ongoing SAE or AE leading to treatment discontinuation and patient is alive at week 12	Ranked above patients who died, but below patients with missing data and no clinical event.	Patient has ongoing SAE or AE leading to treatment discontinuation, no information of week 12 6MWT distance and patient alive at week 12.	-356
3	Patient died before the measurement of 6MWT at week 12 was conducted.	Ranked by time to death from randomization	Patient died y days after randomization	-358+y/1000

Similar rules following the same strategy will be defined in the TSAP to impute missing values for the key secondary endpoints.

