3.3.2 Inclusion criteria

1. Of full age of consent (according to local legislation, usually ≥ 18 years) at screening.
2. Male or female patients. WOCBP¹ must be ready and able to use highly effective methods of birth control per ICH M3 (R2) that result in a low failure rate of less than 1% per year when used consistently and correctly. A list of contraception methods meeting these criteria is provided in the patient information. For sites in Portugal please refer to the contraception methods described in [appendix 10.8](#).
3. Signed and dated written informed consent in accordance with ICH-GCP and local legislation prior to admission to the trial
4. 6MWT distance ≤ 350 m at screening and at baseline.
5. Patients with CHF diagnosed for at least 3 months before Visit 1, and currently in NYHA class II-IV
6. CHF with preserved EF defined as LVEF > 40 % as per echocardiography at Visit 1 per local reading and no prior measurement of LVEF $\leq 40\%$ under stable conditions.
7. Elevated NT-proBNP > 300 pg/ml for patients without atrial fibrillation (AF), OR > 600 pg/ml for patients with AF, as analysed at the Central laboratory at Visit 1
8. Patients must have at least one of the following evidence of HF:
 - a. Structural heart disease² (left atrial enlargement and/or left ventricular hypertrophy) documented by echocardiogram at Visit 1, OR
 - b. Documented HHF³ within 12 months prior to Visit 1

¹ A woman is considered of childbearing potential, i.e. fertile, following menarche and until becoming post-menopausal unless permanently sterile.

A postmenopausal state is defined as no menses for 12 months without an alternative medical cause. Permanent sterilisation methods include hysterectomy, bilateral salpingectomy and bilateral oophorectomy. Please note that tubal ligation is NOT accepted as a method of permanent sterilisation and therefore a woman who underwent tubal ligation is still considered as WOCBP. However tubal ligation is considered as a method of highly effective birth control.

² Structural heart disease is further defined in [appendix 10.7](#)

³ The main reason for HHF must be HF. Documentation for HHF must be provided in the source documents

9. Consistent with prevailing CV guidelines, if oral diuretics are prescribed to control symptoms, patients must be on an appropriate and stable dose of oral diuretics for at least 2 weeks prior to Visit 1 to control symptoms.

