6.2 IMPORTANT PROTOCOL DEVIATIONS

A protocol deviation (PD) is important, if it affects the rights or safety of the study patients or if it can potentially influence the primary outcome measures for the respective patients in a way that is neither negligible nor in accordance with the study objectives.

Important protocol deviations (iPDs) will be described in the clinical trial report (CTR). A listing of patients with medication code broken will be provided.

Table 6.2: 1 Important protocol deviations

| Category / Code | Description | Requirements | Excluded from |
|-----------------|--|--------------------------------|---------------|
| A | Entrance criteria not met | | |
| A1 | Target indication not met | | |
| A1.06 | No chronic HF or no NYHA class II-IV | Inclusion criterion #5 not met | None |
| A1.07 | Conditions on ejection fraction (EF) not met | Inclusion criterion #6 not met | None |
| A1.08 | Conditions on NT-proBNP not met | Inclusion criterion #7 not met | None |
| A1.09 | Conditions on HF not met | Inclusion criterion #8 not met | None |

Table 6.2: 1 Important protocol deviations (cont.)

| Category / Code | Description | Requirements | Excluded from |
|-----------------|--|---|---------------|
| A2/3 | Other entrance criteria not met | | |
| A2.02 | Age out of range | Inclusion criterion #1 not met | None |
| A2.08 | Specific inclusion criterion for women of child-bearing potential not met | Inclusion criterion #2 not met | None |
| A2.14 | 6MWT distance above 350m at screening or baseline or below 100m at baseline | Inclusion criterion #4 or exclusion criterion #10 not met | SensRS1 |
| A2.12 | Inclusion criterion on stable concomitant medication not met | Inclusion criterion #9 not met | None |
| A3.44 | Patient with unstable conditions | Exclusion criteria #1, #2, #6, #9, #13, #18 or #22 not met, inclusion criterion #10 not met | None |
| A3.49 | Participation in another Empagliflozin HF trial | Exclusion criterion #3 not met | None |
| A3.51 | Type 1 diabetes | Exclusion criterion #4 not met | None |
| A3.09 | Renal insufficiency or renal impairment (assessed by eGFR) | Exclusion criterion #5 not met | None |
| A3.33 | Systolic blood pressure at visit 1 or 2 out of range | Exclusion criterion #7 not met | None |
| A3.31 | Atrial fibrillation or atrial flutter with a resting heart rate >110bpm | Exclusion criterion #8 not met | None |

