6.3 SUBJECT SETS ANALYSED

The following patient sets are defined in section 7.3 of the protocol:

- **Randomised set (RS)**
This patient set includes all randomised patients, whether treated or not. Treatment will be evaluated as randomised.
- **Treated set (TS)**
This patient set includes all patients who were dispensed study medication and were documented to have taken at least one dose of investigational treatment. Treatment will be evaluated as randomised.

In addition the following patient set is defined:

- **Screened Set (SCR)**
Consists of all patients screened for the trial, with informed consent given and who completed at least one screening procedure at Visit 1.

For sensitivity analyses the following patients set is defined:

- **Sensitivity analysis set 1 (SensRS1)**
Randomised patients excluding patients with an iPD related to 6MWT, i.e. iPD categories A2.14, G3.48 and G3.49 of [Table 6.2: 1](#)
- **Sensitivity analysis set 2 (SensRS2)**
Randomised patients excluding patients for which at least one on-treatment value of urine glucose test result was included in the safety laboratory reports posted to a portal by the central laboratory, and the reports were accessed before database lock.
- **Sensitivity analysis set 3 (SensRS3)**
Randomised patients excluding non-diabetic patients for which at least one on-treatment value of urine glucose test result was included in the reports posted and accessed before database lock.

Demographics and baseline characteristics as well as the efficacy analysis will be based on the RS. Demographics will be repeated on the TS if the number of patients in the analysis sets differ by more than 5%. The safety analysis will be based on the TS.

Overall number of patients participating in the study (screened, randomised, screened but not randomised, etc.) by region and country will be based on the SCR.

Table 6.3: 1 Subject sets analysed

| Class of endpoint | Subject set | | |
|---|--------------|----------------|----------------|
| | Screened Set | Randomised set | Treated set |
| Primary and key secondary endpoints | | X | X |
| (other) Secondary and further endpoints | | X | |
| Safety endpoints | | | X |
| Demographic/baseline endpoints | | X | X ¹ |
| Extent of exposure | | | X |
| Disposition | X | | |

¹ Demographics will be repeated on the TS if the number of patients in the analysis sets differ by more than 5%.

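### The 6MWT imputation constants keep missing data and deaths below every measured change only if no randomised patient has a baseline above 350 m

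*Protocol*

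**What the plan says.** Protocol 7.5 states the ordering without condition: "All imputed data due to missing data will be lower than measured values". It derives the lowest measurable change, -350 m, from "the highest possible baseline value (350 m), and at week 12 the lowest possible value of 0m". Table 7.5:1 then imputes:

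- -352 + x/1000 when there is a post-baseline value (x is the change to the last available value) and no clinical event;
- -354 for "No information of post-baseline 6MWT distance and no clinical event";
- -356 for an ongoing SAE or an AE leading to discontinuation, with "no information of week 12 6MWT distance and patient alive at week 12";
- -358 + y/1000 for a death y days after randomisation.

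SAP 6.6 repeats the principle for all confirmatory analyses, SAP 6.6.1 takes over the protocol rules by reference, and SAP Table 6.6.3:1 uses -354, -356 and -358 + y/1000 for Week 6.

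The 350 m figure comes from inclusion criterion 4 (Protocol 3.3.2), which applies "at screening and at baseline". SAP Table 6.2:1 lists deviation A2.14, "6MWT distance above 350m at screening or baseline or below 100m at baseline", triggered by "Inclusion criterion #4 or exclusion criterion #10 not met", and excludes the patient from SensRS1 only. Of the randomised set, SAP 6.3 says: "This patient set includes all randomised patients, whether treated or not". SAP 7.4.1 runs the primary analysis on that set.

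A Week 12 visit without a walk can count as a measured 0 m. Protocol 7.5 applies this when the patient cannot walk or when safety concerns prevent the test; SAP 6.6 applies it whenever the visit takes place and the test is not done. The change is then minus the baseline.

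**The concern.** An eligibility limit is treated as if it bounded the data. If a patient is randomised with a baseline above 350 m, nothing in either document caps that baseline, adapts the constants or supplies another rule. The measured change can then fall into or below the band of values reserved for missing data, clinical events and death.

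What is at stake is the defining property of the primary ranking: measured outcomes first, then missing without an event, then missing with an event, then death. For such a patient the numbers could place someone alive and assessed at Week 12 below patients who died, contrary to the order both documents state.

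**Working it through.** **Reproducing the plan's figures.** Inputs from Protocol 7.7: difference 30 m, SD 72 m, two-sided 0.05, power 90%. P(X<Y) = Φ(-30/(72√2)) = 0.384. Noether's formula gives n per group = (1.960 + 1.282)² / [6(0.384 - 0.5)²] = 10.507/0.0807, about 130.1, so 131 as stated. With unrounded probabilities the same formula gives the stated 76 and 50 for 40 m and 50 m. A simulation (20,000 runs, 150 per group, Table 7.5:1 constants for missing patients) gives power of 90.2%, 87.3% and 84.6% at 5%, 8% and 10% missing, against 90%, 87% and 85% in Table 7.7:2.

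**The ordering.** Set the Week 12 value to 0 m, so change = -baseline, and compare with the constants. Category 1 with a Week 6 value runs from about -352.35 to -351.85 for x from -350 to +150 m. Deaths run from -357.999 to -357.908 for y from 1 to 92 days.

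| Baseline (m) | Measured change (m) | Ranks below |
|---|---|---|
| 350 | -350 | no imputed value; the rule works |
| 351 | -351 | no imputed value |
| 353 | -353 | missing with a Week 6 value (about -352) |
| 355 | -355 | also missing with no post-baseline value (-354) |
| 357 | -357 | also missing with a clinical event (-356) |
| 358 | -358 | also every death from day 1 on |

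At exactly 352 m the result depends on the sign of x. The Week 12 value need not be 0 m: any fall of 358 m or more ranks below deaths, for example 400 m to 40 m (-360). In the Week 6 table the first value crossed is -354.

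**Effect on the test.** With 150 per group, the SD of the rank sum is √(150 × 150 × 301/12) = 751.2. With m missing patients in total, the misplaced patient drops at most m ranks:

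- m = 15 (5% of 300): 15/751.2 = 0.02 on the z scale;
- m = 30 (10% of 300): 30/751.2 = 0.04.

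These are ceilings. Each missing patient overtaken moves up one rank, so if they are split evenly between arms the net shift halves, to 0.01 and 0.02.

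**Power, illustrative case.** Assume two patients per arm with baseline 370 m and 0 m at Week 12, and 5% missing. Simulated power is 88.8% with the fixed constants and 88.7% with the intended order, a difference within simulation error.

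**The case against.** Several points on the other side stand.

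- Any walk above 350 m at Visit 1 or 2 makes the patient a screen failure (Flow Chart notes 8 and 9; Protocol 5.1.1). A reader might infer from A2.14 that the SAP expects such patients to be randomised. It does not show that: Table 6.2:1 gives a code to nearly every entry criterion, so the code means the deviation would be tracked. A2.14 also bundles three situations, and only a baseline above 350 m matters here; a screening walk above 350 m or a baseline below 100 m does not disturb the order.
- Several conditions must coincide: the eligibility breach, a fall of about 352 m or more, and at least one missing patient in the category crossed. Ranking below death needs a fall of 358 m or more and at least one death.
- The primary analysis is repeated on SensRS1 (SAP 7.4.2), so any influence of these patients could be seen. This limits the consequence, but removing patients in a sensitivity analysis does not correct their rank in the confirmatory test.
- The intended order is explicit in SAP 6.6 and in the ranking column of Table 7.5:1. That makes this a gap in numerical implementation. It still needs closing, because SAP 6.6.1 directs the analyst to the protocol's fixed values.

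**Conclusion.** As written, the constants do not guarantee the order that both documents promise. For a randomised patient above the 350 m limit who is scored at or near 0 m at Week 12, they can place a measured change below missing data (baseline above about 352 m) and place it below deaths (358 m or more). The arithmetic needs no assumption beyond that combination occurring.

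A reader might infer that the primary result is at risk, or want a probability attached. The documents support neither. They give no count of patients randomised above 350 m and no rate of 0 m scores, so any frequency would be invented. The z shift of at most about 0.02 to 0.04 per patient assumes 15 to 30 missing patients in total; sample size and power are unaffected. The problem is confined to the two 6MWT tables: the KCCQ-TSS and CHQ-SAS constants in SAP 6.6.2 rest on true scale limits and cannot fail this way. This is a minor correction, worth making because it concerns the confirmatory ranking and avoids an after-the-fact decision.

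**What to change.** In SAP 6.6.1 and 6.6.3, define L as the smaller of -350 and minus the largest baseline 6MWT in the randomised set. For Week 12 impute L-2+x/1000, L-4, L-6 and L-8+y/1000 in the existing category order; for Week 6 use the last three. No measured change can be below L, so the stated order always holds. Assigning ranks directly by category would achieve the same for the test, much as SAP 7.4.2 already does for its residual-based analysis.

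Because SAP 6.6.1 relies on the protocol's table, list this in SAP 4.1 as a change from the protocol. The cost is a sentence in each of the two sections and one entry in 4.1. It needs no treatment codes, and it reproduces the present constants exactly (L = -350) when no baseline exceeds 350 m.
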